# HMC RESEARCH PROTOCOL

## 1. Synopsis

This RCT aims to assess the effectiveness of HM Gel (Hydrophilic Methacrylate Gel) and BS (Beta Sitosterol Ointment) in promoting the healing process of episiotomy and CS (cesarean section scars).

Episiotomy and cesarean section are common surgical procedures in obstetrics and gynecology, and scar healing is an important aspect of postoperative recovery. However, there is a lack of evidence comparing the effectiveness of topical treatments specifically for these types of scars. This study seeks to address this research gap by evaluating the effectiveness of Hydrophilic Methacrylate Gel and Beta Sitosterol Ointment in scar healing after episiotomy and cesarean section procedures.

The trial will employ a prospective, randomized controlled design. Adult females who have recently undergone episiotomy or cesarean section procedures will be recruited as participants, and informed consent will be obtained from each participant.

Participants will be randomly assigned to one of two groups: an experimental group receiving Hydrophilic Methacrylate Gel and a control group receiving Beta Sitosterol Ointment. The application of the respective treatments will follow established protocols.

Data collection will involve objective measures and participant-reported outcomes. Parameters such as wound healing progress, scar appearance, pain levels, and patient satisfaction will be assessed at predetermined intervals using standardized assessment tools and scoring systems.

Statistical analysis will be conducted to compare the primary and secondary outcomes between the two treatment groups. Appropriate statistical tests, such as t-tests or chi-square tests, will be employed to analyze the data.

The study will be conducted in adherence to HMC ethical guidelines, ensuring participant safety, privacy, and confidentiality.

The findings of this study will provide valuable insights into the effectiveness of Hydrophilic Methacrylate Gel and Beta Sitosterol Ointment in promoting the healing of episiotomy and cesarean section scars. The results may guide healthcare professionals in selecting optimal topical treatments for scar management, ultimately improving patient outcomes and satisfaction in the context of these surgical procedures.

## 2. Abbreviations and Acronyms

RCT: Randomized Controlled Trial  
HM Gel: Hydrophilic Methacrylate Gel  
BS Ointment: Beta Sitosterol Ointment  
CS: Cesarean Section  
HMC: Hamad Medical Corporation

## 3. Introduction / Background

Episiotomy and cesarean section (CS) are common surgical procedures in obstetrics and gynecology, often performed to safeguard the well-being of both mothers and newborns (1). Adequate wound healing and effective scar management are vital components of postoperative care, profoundly influencing patient recovery, comfort, and long-term quality of life (2). However, despite the significance of these aspects, the current body of literature presents a noticeable gap in real-world evidence regarding the effectiveness of topical treatments specifically tailored for post-episiotomy and CS scars.

The absence of well-established treatment protocols, coupled with the limited research in this area, presents significant challenges for healthcare professionals tasked with selecting the most suitable interventions for scar management. Current standard practices typically involve the use of emollients, moisturizers, and silicone-based products (3). However, the empirical evidence supporting their efficacy in promoting wound healing and enhancing patient satisfaction remains inconclusive (4, 5).

In the specific context of Al-Wakra Hospital, we conduct an average of approximately 350 deliveries each month, which includes both cesarean sections and normal deliveries with episiotomy procedures. This significant volume of procedures highlights the relevance and importance of investigating the most effective scar management interventions.

In our standard clinical practice at Al-Wakra Hospital, emollient, moisturizer such as betasitosterol is commonly used for scar management.

The local healthcare system in Qatar and Al-Wakra Hospital is committed to providing the highest standard of care to its diverse patient population. Given the substantial number of patients undergoing episiotomy and cesarean section procedures, optimizing scar management is imperative to improve patient outcomes and enhance overall healthcare quality.

The present research seeks to bridge this knowledge gap by conducting a rigorous clinical trial to evaluate the potential benefits of novel scar management interventions for post-episiotomy and CS scars. In particular, this study focuses on the effectiveness of Hemagel Ointment, a topical hydrophilic methacrylate gel that has demonstrated promise in wound healing and scar management across various clinical settings (6). Hemagel's hydrophilic nature allows it to create a moist wound environment, which aligns with established principles of wound healing (7).

## HMC RESEARCH PROTOCOL

Additionally, its mechanism of action involves the formation of a protective barrier over the wound site, potentially reducing infection risk and facilitating a controlled healing process (8).

While some studies have explored the application of Hemagel Ointment in wound healing, its specific effects on post-episiotomy and CS scars remain relatively uncharted territory. Consequently, there exists a compelling need to conduct well-designed clinical trials that rigorously assess Hemagel Ointment's efficacy and safety in the context of these surgical procedures.

Therefore, the aim of this study is to evaluate the effectiveness and safety of Hemagel Ointment in post-episiotomy and cesarean section scar care through a randomized clinical trial. This trial will provide comprehensive evidence regarding the effectiveness of Hemagel Ointment in promoting wound healing, alleviating pain, improving scar appearance, and enhancing patient satisfaction in these specific contexts.

By conducting a rigorous randomized clinical trial, we seek to generate high-quality data that will inform clinical practice and guide healthcare professionals in selecting optimal interventions for scar management in post-episiotomy and cesarean section cases. This research will contribute to the existing body of knowledge in scar care and provide valuable insights for healthcare professionals, ultimately improving patient outcomes.

The results of this study have the potential to facilitate evidence-based decision-making, facilitate personalized patient care, and potentially reduce the burden of complications associated with post-episiotomy and cesarean section scars. Furthermore, the findings will contribute to advancing the field of scar management and may pave the way for future research and the development of targeted interventions.

### 4. Objectives

- 1- The primary objective of this trial is to evaluate the effectiveness of Hemagel Ointment in promoting wound healing and reducing complications among patients who have undergone episiotomy or cesarean section procedures. The assessment of wound healing will be conducted using a validated assessment tool, which is included as an attachment.
- 2- The secondary objectives of this study involve assessing the impact of Hemagel Ointment on pain management, scar appearance, and patient satisfaction. To measure pain levels, standardized pain scales will be utilized, allowing for a

## HMC RESEARCH PROTOCOL

comparison of the effectiveness of Hemagel Ointment in alleviating pain compared to the control group. Furthermore, scar appearance will be evaluated using the Patient and Observer Scar Assessment Scale (POSAS), which is a validated tool designed to assess cosmetic outcomes. Patient satisfaction will be assessed through questionnaires, which are provided as an attachment.

Additionally, standardized pain scales will be employed to assess pain levels, and the attached scale provides further details on this measurement.

### 5. Indicate if this is a retrospective data review

- ☒ **Prospective study**

**Provide the date range of the chart review:** RCT

### 6. Study Methodology

The proposed study is a prospective, randomized controlled trial (RCT) that aims to compare the effectiveness of two topical treatments, HM Gel (Hydrophilic Methacrylate Gel) and BS Ointment (Beta Sitosterol Ointment), in promoting the healing process of episiotomy and cesarean section scars. The study will include two groups: an experimental group receiving HM Gel and a control group receiving BS Ointment.

**Sample size calculation or justification of numbers:** A priori sample size calculation will be conducted to determine the required number of participants for adequate statistical power. This calculation will consider factors such as the expected effect size, desired level of significance, power of the study, and anticipated dropout rate. We aim to recruit enough participants to ensure the statistical validity and generalizability of the study results.

The sample size for this study was determined based on the desired level of statistical power (80%) and the significance level (0.05). Since no prior estimates of effect size were available, a moderate effect size was assumed. Using a two-sample t-test, the sample size per group was calculated to be 53 participants in patients with cesarean section. Considering rounding up to the nearest whole number, a total sample size of

106 participants was determined for the 2 groups of cesarean section, and the same number for patients (53) with episiotomy, a total of 106 participants was determined for the 2 groups of vaginal delivery with episiotomy. This sample size calculation ensures that the study will have sufficient power to detect meaningful differences in pain levels and wound healing outcomes.

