### 10. Statistical Consideration and Data Analysis :

#### Randomization and Allocation Concealment:

We will be blinding the tube ointments to ensure impartiality in the assessment of efficacy between the two treatments. This adjustment will enable us to minimize potential biases and ensure the integrity of our results.

The ointment tubes will be packaged in identical outer packaging, such as opaque boxes, to conceal any distinguishing features.

This approach will ensure that the participants nor the assessors of wound know which ointment is being used. Blinding of data analysts will help ensure impartiality during the analysis process.

Randomization: We will indeed use computer-generated random numbers or randomization software to ensure unbiased and unpredictable allocation. Instead of stratifying during randomization, we will collect comprehensive data on age group, BMI, and type of surgery. Subgroup analyses will be conducted during data analysis, allowing for a thorough examination of treatment effects within specific subgroups.

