#### Statistical Analysis Plan:

The statistical analysis plan will be as follows:

- **Descriptive Statistics:**  
Descriptive statistics will be used to summarize the demographic and baseline characteristics of the participants in both groups. Continuous variables, such as age and BMI, will be presented as means with standard deviations or medians with interquartile ranges, depending on their distribution. Categorical variables, such as parity and type of surgery, will be summarized as frequencies and percentages.
- **Primary Outcome Analysis:**  
The primary outcome of wound healing will be analyzed using appropriate statistical methods. As the wound healing outcome is likely to be a categorical variable (e.g., healed/not healed), we will employ the chi-square test or Fisher's exact test, depending on the expected cell frequencies, to compare the proportions of healed wounds.

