## HMC RESEARCH PROTOCOL

between the two treatment groups.

- **Secondary Outcome Analysis:**

For secondary outcomes, such as pain management, scar appearance, and patient satisfaction, we will use similar statistical methods. Pain management and patient satisfaction may be assessed using standardized pain scales and questionnaires, respectively. Depending on the distribution of the data, we will utilize t-tests or Mann-Whitney U tests to compare continuous variables and chi-square tests or Fisher's exact tests for categorical variables.

- **Intention-to-Treat (ITT) Analysis:**

The primary analysis will be conducted on an intention-to-treat (ITT) basis, including all randomized participants. This approach accounts for protocol deviations and maintains the randomization balance between the groups. Participants will be analyzed according to their allocated treatment group, irrespective of protocol adherence or completion.

- **Subgroup Analyses:**

We will perform subgroup analyses to explore potential effect modifiers, such as age, BMI, or parity, on the treatment outcomes. Interaction tests or stratified analyses may be employed to investigate the impact of these factors on the primary and secondary outcomes.

- **Statistical Software:**

All statistical analyses will be performed using a reputable statistical software package, such as SPSS or R. These software tools are widely used for data analysis and will provide reliable results for this study.

- **Statistical Significance:**

Statistical significance will be defined as a p-value less than 0.05. Results with p-values less than this threshold will be considered statistically significant, indicating a significant difference between the treatment groups.

- **Who Will Perform the Analysis:**

The data analysis will be carried out by qualified statisticians [name] (HMC biostatistician) with expertise in statistical methods. These individuals will be independent of the study's clinical team and will be blinded to the treatment allocation to ensure unbiased analysis.

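### The trial is sized separately for each surgery type but the primary analysis reads as one pooled comparison, and no rule says which result decides

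*Combined protocol and SAP*

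**What the plan says.** **Sizing (section 6, sample size).** Power is 80% and the significance level 0.05. The effect is given only in words: "Since no prior estimates of effect size were available, a moderate effect size was assumed". The calculation is then done by surgery type: "Using a two-sample t-test, the sample size per group was calculated to be 53 participants in patients with cesarean section". The same number is taken for episiotomy: "a total of 106 participants was determined for the 2 groups of vaginal delivery with episiotomy". That makes 212 women, raised to about 60 per group for dropout.

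**Primary analysis (section 10, Statistical Analysis Plan).** Healing is expected to be a healed/not healed variable. A chi-square or Fisher's exact test is chosen "depending on the expected cell frequencies, to compare the proportions of healed wounds" between the two treatment groups. The intention-to-treat paragraph puts all randomised participants into the primary analysis. Surgery type is not mentioned in either place.

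**Surgery type elsewhere.** Section 7 (Stratification) randomises independently within surgery type. Section 10 (Randomization and Allocation Concealment) drops stratification, lists surgery type with age and BMI as data to collect, and adds: "Subgroup analyses will be conducted during data analysis, allowing for a thorough examination of treatment effects within specific subgroups". The subgroup paragraph of the Statistical Analysis Plan gives age, BMI and parity as examples and does not name surgery type.

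**Significance rule (section 10).** "Statistical significance will be defined as a p-value less than 0.05", followed by: "Results with p-values less than this threshold will be considered statistically significant, indicating a significant difference between the treatment groups". No order of testing, split of alpha or rule for trial success appears.

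**The concern.** Sizing each surgery type for its own 80% power makes sense if each is to give its own answer. The analysis text reads as one answer for both types together. That leaves three candidate contrasts for the primary outcome: caesarean, episiotomy and pooled. The significance rule treats a p-value below 0.05 the same way for all three.

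Two things are at stake. If the products do not differ, reporting whichever contrast reaches 0.05 gives more than a 5% chance of a false claim. If they do differ, the headline can depend on a choice of contrast that the plan leaves open until the data are seen.

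**Working it through.** **1. The plan's own figure.** The inputs from section 6 are a two-sample t-test, alpha 0.05 and power 80%. The effect size and sidedness are not given.
- Two-sided, d = 0.55: 52.9, so 53 per arm. This matches.
- Two-sided, d = 0.50: 63.8, so 64 per arm. Power at 53 per arm is 72%.
- One-sided, d = 0.50: 51 per arm.

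So 53 can be matched but not uniquely reproduced. With 10% dropout, 53/0.90 = 58.9, in line with about 60 per group. For a pooled test, 2 × 53 = 106 per arm gives about 95% power at d = 0.50, well above the stated 80%. The sizing therefore fits separate comparisons, not a pooled one.

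**2. False-positive rate, no product difference, each test two-sided at 0.05.** The surgery types contain different women, so their tests are independent.
- Pooled test alone: 5%.
- Either surgery-type test: 1 − 0.95² = 9.75%.
- Either of those or the pooled test, with equal-sized types and Z_pooled = (Z_CS + Z_Epi)/√2: 1 − P(all three |Z| < 1.96) = 11.5%, by numerical integration and confirmed by simulation.
- Both surgery types required: 0.05² = 0.25%.

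With the planned chi-square test, at 53 or 60 per arm and assumed healing rates from 50% to 95%, simulation gives 8.5–10.7% for two tests and 10.2–12.0% for three. Counting only false claims in favour of HM Gel, the rates are 4.9% and 5.8%, against 2.5%. The normal-theory rates do not depend on the effect size.

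**3. How often the contrasts differ on significance.** Assumptions: d = 0.5 in caesarean women and 0 in episiotomy women; 60 × 0.90 = 54 evaluable per arm per type; normal approximation.
- Caesarean: mean of Z = 0.5 × √(54/2) = 2.598; power = Φ(2.598 − 1.960) = 74%.
- Pooled: mean of Z = 2.598/√2 = 1.837; power, both tails, = 45%.
- Caesarean significant and pooled not: 31.3%. Pooled significant and caesarean not: 2.6%. Total about 34%.
- Both the caesarean and pooled tests significant: 73.8% − 31.3% = 42.5%, about 43%.

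The same steps under other inputs:

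| d, caesarean only | Evaluable per arm per type | Mean of Z, caesarean | Caesarean power | Pooled power | Differ |
|---|---|---|---|---|---|
| 0.50 | 54 | 2.598 | 74% | 45% | 34% |
| 0.55 | 54 | 2.858 | 82% | 52% | 33% |
| 0.50 | 27 | 1.837 | 45% | 25% | 28% |

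The last row applies if about 60 per group means 60 per arm over both types: 30 × 0.90 = 27.

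**4. Hypothetical counts with the planned chi-square test.** Caesarean 45/53 v 35/53, p = 0.024. Episiotomy 42/53 v 42/53, p = 1.0. Pooled 87/106 v 77/106, p = 0.10. On the same data, the caesarean test is significant and the pooled test is not.

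**The case against.** The best defence is that section 10 already points to an answer: one test between the two treatment groups, all randomised participants in the primary analysis, and surgery type left to subgroup analyses described as exploring effect modifiers. On that reading the pooled test decides, the error rate is 5%, and the significance rule only defines the term for a single result, not success for the trial. Much of this stands. A reader might infer that the plan is silent on its primary contrast; it is not. What the defence does not explain is the sizing in section 6, and no sentence makes the surgery-type results supportive.

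Two other strong readings also fail. A reader might infer that the plan carries an error rate of about 10–11%. That needs a rule that any one significant contrast is enough, which the wording permits but does not state. A reader might also infer that the contrasts give opposite answers, or clash in some 41% of trials when d = 0.5 in both types. The disagreement worked out here is significant versus not significant, not a reversal of direction. The 41% counts trials where the pooled test succeeds and the two types do not both succeed, so it needs a rule that both must succeed, under which the null error is 0.25%. Under the either-is-enough rule that produces 9.75%, pooled significant with neither type significant occurs in only 3.6% of trials. The two figures cannot be used together.

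The pooled and caesarean tests also ask different questions, so some disagreement is expected. That is a reason to say beforehand which question is primary.

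**Conclusion.** The point holds as an unreconciled conflict with no decision rule. The per-type sizing in section 6, the pooled reading of the Statistical Analysis Plan and the subgroup role given to surgery type in section 10 do not fit together, and the significance rule does not limit which contrast may carry the claim.

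Its size is conditional: 5% if the pooled test alone decides, 9.75% if either surgery-type test may count, 11.5% if any of the three may. These figures assume two-sided tests; three tests also assumes types of equal size. The 34% disagreement further assumes an effect in caesarean women only, d = 0.5 and 54 evaluable per arm per type, none of which the plan states, and it uses a continuous-scale approximation although a binary outcome is expected. It illustrates the conflict and is not a prediction. The matter should be settled before unblinding because it bears on the headline conclusion and can be resolved in text.

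**What to change.** 1. **Primary Outcome Analysis, section 10.** Name one primary contrast: HM Gel versus BS Ointment in all randomised women, stratified by surgery type, two-sided 0.05. A Cochran-Mantel-Haenszel test could replace the unstratified chi-square or Fisher test.
2. **Surgery-type results.** Report caesarean and episiotomy results as estimates with 95% confidence intervals and no stand-alone significance claim. As an optional extension, test each at 0.05 only after the pooled test succeeds. This is valid without splitting alpha, because the pooled test covers the joint null of no difference in either type.
3. **Statistical Significance, section 10.** For the healing outcome, limit the claim of a significant treatment difference to the primary contrast and, if adopted, to tests reached in that order.
4. **Section 6.** State that the per-type sizing supports the surgery-type estimates and does not define two further primary tests.

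This needs wording only, with no extra patients or data. The cost is in power. If the product works in one surgery type only, the pooled test has about 45% power against 74% for a separate caesarean test under the assumptions above, and with the optional gate the caesarean claim succeeds in about 43% of trials. If the investigators do want two separate answers, they should say so and control the error: at 0.025 each the family-wise rate is 1 − 0.975² = 4.94%, but 80% power then needs 65 per arm per type at d = 0.55, or 78 at d = 0.50.

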#### **Dropout Rate:**

The anticipated dropout rate is indeed an important consideration in sample size determination. We recognize the potential for participant attrition during the course of our study. To

## HMC RESEARCH PROTOCOL

address this concern and to ensure the robustness of our findings, we have factored in an anticipated dropout rate of 10% in our sample size calculation. While this rate is conservative and aligned with similar clinical trials, we understand the importance of minimizing the impact of dropout on our study's outcomes.

